12. PUBLICATION OF RESEARCH FINDINGS

Publication of the results of this trial will be governed by the policies and procedures developed by the Publication Subcommittee of the Steering Committee. Presentations, abstracts, or manuscripts will be submitted to PCORI within 30 days of acceptance.

## **1. Introduction**

C3FIT is a cluster -randomized clinical trial randomizing 24 sites (21 of which provided data and will be included) to assess the effectiveness, defined at 12-months post-stroke discharge, of post-stroke care delivered using the Joint Commission (JC)-certified Comprehensive or Primary Care (CSC/PSC) model compared to an integrated, coordinated, technology-enabled Integrated Stroke Practice Unit (ISPU) model (that includes CSC/PSC care). The trial has two primary outcomes, the modified Rankin score (mRS) and the Stroke Impact Scale (SIS), both assessed at baseline (for SIS, only in approximately 50% of the participants), and at 3, 6 and 12 months. Any beneficial treatment effect of the ISPU approach on the mRS and SIS is presumed to be through a beneficial effect on “intermediate” factors, specifically better control of: 1) systolic blood pressure (SBP) to levels below 130 mmHg, 2) LDL levels to levels below 70 mg/dL, 3) HbA1c to levels below 7%, 4) smoking cessation, 5) adherence to AHA diet guidelines by following a Mediterranean-type or DASH diet, and 6) adherence to AHA exercise guidelines by a usual exercise level of moderate or above. Each of these intermediate factors will be assessed among those failing to be in control at hospital discharge (i.e., for SBP, among those with discharge SBP $\geq$ 130 mmHg; for LDL, among those with discharge LDL levels above 70 mg/dL, etc.). Because of this presumed pathway for potential effects, the assessment of treatment effects on these six intermediate factors is considered an integral part of the assessment of primary outcomes. Because the cluster-randomization may fail to balance the treatment groups on key factors potentially affecting outcome, treatment differences will be assessed after a series of incremental models, first in a crude model with no adjustment, then with adjustment for measures of stroke severity, then with further adjustment for demographic factors, and then with further adjustment for major cardiovascular risk factors. Treatment differences for both the two primary outcome variables and the six intermediate factors will be assessed using a mixed model approach including the assessments at baseline, 3 months, 6 months and 12 months.

Beyond the intermediate factors above, the study also has secondary outcomes including mortality, recurrent stroke, rehospitalization, time at home, depression, caregiver strain, and perceived support.

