- (1) The ISPU approach will improve secondary stroke outcomes relative to the CSC/PSC approach, including: SIS and smRS at 3 and 6 months, risk factor control, stroke recurrence rates, hospital readmission rates, mortality in the first 12 months, time at home, patient depression, and caregiver strain.
- (2) The ISPU benefit in SIS and smRS will persist after the protocol-based post-acute coordination of in-home/facility care is terminated (at 12 months).
- (3) Patient characteristics (specifically age, race, sex, income, and education) will affect the primary or secondary intervention differences.

B. Primary and Secondary Outcomes

Primary and secondary outcomes are documented in Table 1 and described below.

- *Primary outcomes* include patient function and QOL using the SIS and smRS at 12-months post-stroke.
- *Secondary outcomes* are patient/caregiver-centered and include: (1) short-term patient function and QOL using the SIS and smRS (at 3 and 6 months); (2) the proportion of patient with risk factors controlled at target (at 3, 6, and 12 months); (3) mortality in the first 12 months, time to first recurrent stroke, and number of hospital readmissions per participant month over the first 12 months; (4) Time At Home (proportion of survival time spent at home); (5) patient depression, using the Patient Health Questionnaire (PHQ-9; at 3, 6, and 12 months); and (6) caregiver strain, using the Caregiver Strain Index (CSI; at 3, 6, and 12 months).

Table 1. Study Outcome Measures and Assessment Frequency					
C3FIT OUTCOMES	VARIABLES	ASSESSMENT FREQUENCY (By Month)			
		H	3	6	12
Functional Assessment	Stroke Impact Scale	X	X ⁺	X ⁺	X ⁺
Quality of Life	Simplified Modified Rankin Scale	X	X ⁺	X ⁺	X ⁺
Stroke Risk Factors					
(1) Blood pressure control at target*	Standard Systolic and Diastolic Measurement	X	X	X	X
(2) Lipid control at target*	Standard Lipid Panel or, at a minimum, LDL (Blood Draw, repeated only if patient's cholesterol is elevated at baseline, if LDLC%≥70mg/dl, or if patient is on a statin)	X	X	X	X
(3) Diabetes control at target*	Standard HBA1c (Blood Draw, repeated only if patient's blood glucose is elevated at baseline or if HBA1C%≥7mg/dl)	X	X	X	X
(4) Smoking status*	Question(s) to assess patient smoking status	X	X	X	X
(5) Body Mass Index (BMI)*	Weight and hip circumference	X	X	X	X
(6) Diet	Question(s) to assess patient adherence to recommendations of the American Heart Association (AHA).	X	X ⁺	X ⁺	X ⁺

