9. STATISTICAL CONSIDERATIONS

C3FIT will compare the effectiveness of the JC-certified CSC/PSC care system with the ISPU care system in improving patient outcome and quality of life post-stroke. The primary outcome is the SIS-3.0 at 12 months, while assessment at 3 and 6 months are part of secondary outcomes. The primary analysis will focus on intervention differences in mean SIS score at 12 months. Mixed models will be used to assess the SIS outcome at 12 months, allowing the hierarchical nature of the data to be reflected (patients within Sites), and providing an accounting for data that are not missing completely at random. We anticipate (and trust) that randomization will balance potential confounding factors; however, secondary analysis will be performed with adjustment for baseline factors that could be imbalanced and potentially confound the estimated intervention differences, specifically adjusting for factors assessed at baseline that are known to be strongly associated with stroke outcomes (specifically age and stroke severity). Patients who die or cannot return due to morbid conditions will be assigned to “floor” score for poor outcome (and hence does not reduce the number of evaluable patients). With these patients not representing missing data, we anticipate there will be relatively little additional missing data and that these data will be generally missing at random (i.e., patients not returning because of other conditions, like moving); however, missing data that is present will be addressed by including baseline, 3, and 6 month data in the model and allowing the mixed model to adjust estimates for the missing data at 12 months by incorporating information available through the correlation between measurements.

A. Sample Size

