### **3. Primary Outcome Analyses**

#### **3.1. Analysis of intermediate factors**

Because the ISPU intervention was targeted to specific groups determined by baseline assessments, the primary analysis of the six intermediate factors will be restricted to the estimation of treatment differences among patients who were not in control at discharge, specifically assessing the percentage of patients with:

- 1) SBP below 130 mmHg at 3, 6, and 12-months among those with SBP of 130 mmHg or above at discharge
- 2) LDL below 70 mg/dL at 3, 6, and 12-months among those with LDL of 70 mg/dL or above at discharge

- 3) HbA1c below 7% at 3, 6, and 12 months among those with HbA1c of 7% or above at discharge
- 4) Smoking cessation at 3, 6, and 12-months among those smoking at dischargement,
- 5) Adhering to a Mediterranean or DASH diet among those not adhering at baseline
- 6) Having regular exercise levels of moderate or above among those with lower levels at baseline.

The primary hypothesis will focus on compliance/adherence at the 12-month visit, but mixed models will be used with assessments at the 3 time points (3, 6, and 12 months) and treatment differences reported at all three follow-up times.

Analyses will generally take the approach of using a mixed model approach with: 1) repeated measures at 3, 6 and 12 months, and 2) a random effect for patient and site (if models do not converge, site will be considered as affixed effect). As all of the intermediate factors will be dichotomized for the follow-up assessments, outcomes will be assessed using PROC GLIMMIX. Treatment differences will be assessed in a series of incremental models: 1) crude, 2) adjusted for stroke severity, 3) further adjustment for demographics, and 4) adjustment for cerebrovascular risk factors (see section 2 for factors in each group). The temporal pattern of treatment differences at 3, 6 and 12-months will be described by the treatment-specific proportion adherent/compliant with 95% confidence intervals. The primary assessment of treatment efficacy will be the p-value and confidence intervals for the treatment difference in the proportion at the 12th months; however, p-values and confidence intervals for months 3 and 6 will also be reported.

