### **3.2. Modified Rankin Score (mRS)**

The mRS is a 7-point scale, ranging from 0 (normal) to 6 (dead), where at baseline the scores were from 0 to 5 (discharged dead were excluded from the study). During follow-up, patients were scored a 6 at the 3, 6 and 12-month follow-up if the patient died before the respective follow-up (even if the patient missed intervening visits). The mRS will be dichotomized as “good outcomes” of 0 to 2 points, and “poor outcomes” of 3 to 6 points. Analysis will use a mixed model approach (implemented through GLIMMIX) with the treatment-specific proportion of “good outcomes” modeled at months 0, 3, 6, and 12 (reported with the p-value for treatment differences at each time point). The primary outcome will be treatment differences in the change in the proportion with good outcomes between months 0 and 12, but differences to months 3 and 6 will also be estimated. These differences will be estimated with the same 4-level incremental adjustments, and with both unadjusted and inverse-probability weighted adjustment. Effect modification will be assessed by age, sex, race/ethnicity, stroke sub-type, stroke severity (discharge NIHSS dichotomized at 0 to 1 versus 2+), and nSES. With the discharge mRS as an outcome, the analysis will not be adjusted for baseline mRS.

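### The SAP does not define a positive trial: it sets no deciding model, alpha or success rule for mRS and SIS, and gives primary wording to six outcomes that the protocol lists as secondary

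*SAP*

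**What the plan says.** **Which outcomes are primary.**
- SAP Section 1 names two primary outcomes, mRS and SIS. It then says that assessing "treatment effects on these six intermediate factors is considered an integral part of the assessment of primary outcomes", and introduces the secondary outcomes as those beyond these factors.
- SAP Section 3.1, under the Primary Outcome Analyses heading, says of the six factors: "The primary hypothesis will focus on compliance/adherence at the 12-month visit". It adds: "The primary assessment of treatment efficacy will be the p-value and confidence intervals for the treatment difference" at month 12.
- Protocol Section 1.B lists "the proportion of patient with risk factors controlled at target" among the secondary outcomes.
- The opening of Protocol Section 9 states: "The primary outcome is the SIS-3.0 at 12 months". The Summary, Sections 1.A and 1.B, and Section 9.B name both SIS and smRS. The ISPU and CSC/PSC versions of the protocol agree on all of this.

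**Which analysis decides.**
- SAP Section 3.1 sets four incremental models: crude, then adding stroke severity, demographics and risk factors. Section 3.2 says mRS differences are "estimated with the same 4-level incremental adjustments, and with both unadjusted and inverse-probability weighted adjustment". Section 3.3 does the same for SIS.
- SAP Section 3.1 settles the weighting: where weighted and unweighted interpretations differ, the weighted one is primary.
- Protocol Section 9 describes the mixed model for the primary analysis and calls adjustment for baseline factors (age and stroke severity) a secondary analysis.

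**What counts as success.** Neither document states a significance level, a multiplicity method, a testing order, or whether one or both primaries must succeed. The only p threshold in the SAP is 0.10, for an interaction in the time-at-home analysis (Section 4.2).

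**The concern.** A reader holding the final tables could not tell from the plan whether the trial had succeeded. Counting month 12 only, there are 8 outcomes x 4 models = 32 results that carry primary wording or belong to an outcome that does. Nothing in the SAP ranks the outcomes or the models.

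Model choice is a live question here. SAP Section 1 itself warns that cluster randomization may leave the arms unbalanced on important factors, and 21 sites contribute data. If the crude and adjusted results disagree, the SAP does not say which is the trial's answer. A positive smoking or LDL result could likewise be reported as a primary finding, although the protocol never gave it that status.

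**Working it through.** **1. What the stated power assumes.** Inputs from Protocol Section 9.A: SD 8, 900 patients per arm, 100 per site (so 18 sites), ICC 0.05 or 0.10. With m patients per site and n per arm:

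SE = SD x sqrt(2 x [1 + (m − 1) x ICC] / n)

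At ICC 0.05, SE = 8 x sqrt(2 x 5.95 / 900) = 0.92. Solving for the detectable difference with a noncentral t on 16 df at two-sided 0.05:

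| ICC | Power | Protocol | Recomputed |
|---|---|---|---|
| 0.05 | 80% | 2.7 | 2.745 |
| 0.05 | 90% | 3.2 | 3.178 |
| 0.10 | 80% | 3.7 | 3.716 |
| 0.10 | 90% | 4.3 | 4.302 |

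The figures reproduce. A normal approximation does not fit: at ICC 0.05 it gives 2.58 and 2.98 two-sided, and 2.29 and 2.69 one-sided. The stated power is therefore for a single SIS test at a full two-sided 0.05. The documents never state that level. It is inferred from this match and from the 95% confidence intervals in the SAP.

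**2. One model per outcome, success on any one outcome.** For k independent tests the error is 1 − 0.95^k:
- k = 2: 1 − 0.9025 = 9.75%
- k = 8: 1 − 0.6634 = 33.7%

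The outcomes will be correlated, and the documents give no correlation, so a range is assumed. With equicorrelated normal test statistics (400,000 draws):

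| Correlation | 2 outcomes | 8 outcomes |
|---|---|---|
| 0 | 9.75% | 33.7% |
| 0.3 | 9.5% | 29.9% |
| 0.5 | 9.1% | 25.1% |
| 0.7 | 8.3% | 19.0% |

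These count false results in either direction. Counting only those that favour ISPU (nominal 2.5%), two independent outcomes give 1 − 0.975² = 4.9%. Eight give 18.4% if independent and 9.6% at correlation 0.7.

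**3. Free choice among four models, one outcome.** The assumed correlation between the models' test statistics is 0.95, 0.90 or 0.80. The error is 8.0%, 9.3% or 11.3%.

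**4. Both freedoms together.** Over the same ranges, two outcomes give 13% to 22% and eight give 28% to 62%.

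**5. Both mRS and SIS required, one prespecified model.** A false claim then needs a false rejection of at least one true null that is itself tested at 0.05, so the error is at most 5%.

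**6. Cost of splitting alpha.** Inputs: 1,262 patients (protocol Summary), 21 sites (SAP Section 1), assumed equal in size and split evenly by arm; ICC 0.05; SD 8; 19 df. Then m = 1,262/21 = 60.1, the design effect is 1 + 59.1 x 0.05 = 3.95, and SE = 8 x sqrt(2 x 3.95 / 631) = 0.90.

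| Two-sided alpha | Detectable SIS difference, 80% power | Power at 2.7 |
|---|---|---|
| 0.05 | 2.65 | 82% |
| 0.025 | 2.96 | 72% |

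**The case against.** The strongest reply is that the documents leave less open than a quick reading suggests. Much of it stands.

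- *A reader might count 64 free results, doubling the 32 for weighting.* The documents do not support this. SAP Section 3.1 makes the weighted analysis decide when interpretations differ, so a team that follows the rule gains almost no choice from weighting. Two loose ends remain: it is not defined when interpretations differ, and the rule is written for the six factors and reaches mRS and SIS only by reference.
- *A reader might infer that no text anywhere chooses a model.* Protocol Section 9 does call the adjusted analysis secondary. The gap is that the SAP lists four models without repeating or replacing that ranking.
- *A reader might say that the SAP declares eight primary outcomes.* It says two, and separates them from the six factors, which it presents as the presumed pathway of effect. Eight is a fair reading of Section 3.1, but not the only one.
- *A reader might say that Protocol Section 9 makes SIS the sole primary.* Its opening does; Section 9.B names both. The section is inconsistent with itself.
- *The primary hypothesis joins SIS and smRS with an and.* If that means both must succeed in one fixed model, there is no inflation. This is a possible reading, but neither document states it as a decision rule, and it would not settle which of the four models applies.

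**Conclusion.** The point holds: the plan does not fix what a positive primary result is. Three things are missing: a deciding model in the SAP, a success rule with its alpha or testing order, and a status for the six factors that agrees with the protocol.

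The size depends on how the gap is filled. Under an any-one-outcome rule at two-sided 0.05 with one model each, the false-positive chance is 8.3% to 9.75% for mRS and SIS and 19% to 34% for eight outcomes. Free choice among four models gives about 8% to 11% for a single outcome. The correlations behind these ranges are assumptions, as is the 0.05 level. A flat statement that the trial carries a one-in-three error rate would go too far, because 33.7% needs eight primaries, independence and an any-one rule together. Nor do the documents show any intention to choose the most favourable result; they only fail to rule it out.

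This should be corrected before arm-level results are seen, because it governs the trial's main claim.

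**What to change.** 1. **One deciding analysis per primary outcome.** Name the model and the weighting. Either keep the protocol's unadjusted mixed model, or choose an adjusted one and declare it a change from the protocol. Label all other models as sensitivity analyses. Since the SAP already reports that 21 sites provided data, record that the choice was made before arm-level results were seen.
2. **A success rule with its alpha.** State the significance level and choose one of: SIS first, with mRS tested only if SIS is significant; Holm across the two; or both required. SIS is the natural first test, because it is the only outcome for which Protocol Section 9.A gives detectable differences. Make the opening of Protocol Section 9 agree with Section 9.B.
3. **The six factors.** Return them to secondary or mechanistic status, as in Protocol Section 1.B, and remove the primary wording from SAP Section 3.1.

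**Cost.** No further data collection is needed; it takes SAP wording, a short protocol clarification, and the record described in item 1. The fixed sequence costs SIS nothing. At Holm's first step (0.025) the 80%-power detectable SIS difference rises from 2.65 to about 2.96, and power at 2.7 falls from 82% to 72%. Requiring both needs no alpha split, but the power to win on both cannot exceed that for SIS alone (82% at 2.7), and the documents give no mRS assumptions from which to compute it. All these figures assume equal site sizes.

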## **2. Definitions and classification of covariates**

The covariates used in the incremental models include measures of stroke severity, demographic factors, and traditional cerebrovascular risk factors.

- Measures of stroke severity
  - Discharge location, classified as discharged home vs. not home (skilled nursing, rehabilitation center, etc.).

- Discharge mRS, categorized as 0, 1, 2, 3 or 4 or more (noting relatively few patients with discharge mRS of 5).
- Discharge NIH Stroke Scale (NIHSS), categorized into approximate quartiles of 0, 1, 2-4 or 5+
- Stroke subtype (hemorrhage vs. infarction)
- Demographic factors
  - Age, considered as a continuous factor
  - Male sex
  - Race/Ethnicity, categorized as non-Hispanic white (NHW) versus not NHW (including both other races and Hispanic participants)
  - A summary neighborhood index of socio-economic status (nSES) based on previously published methods, including six variables representing wealth/income, education and occupation: (1) log of median household income, (2) log of median value of owner-occupied housing units, (3) proportion of households receiving interest, dividend, or net rental income, (4) proportion of adults aged  $\geq 25$  years with a high school diploma, (5) proportion of adults aged  $\geq 25$  years with college degree, and (6) proportion of people employed in executive, managerial or professional occupations.
- Baseline cerebrovascular risk factors
  - Cigarette smoking, categorized as current vs. non-current (past or never)
  - Hypertension as a dichotomous variable
  - Dyslipidemia as a dichotomous variable
  - Diabetes as a dichotomous variable
  - Atrial fibrillation or irregular heartbeat as a dichotomous variable
  - Sedentary activity (defined as a score of 0-No Physical Activity or 1-Sedentary or sitting most of the time)

Because the mixed models will include baseline assessment of the outcome variable (i.e., outcomes include measures at times 0, 3, 6, and 12 months), covariates directly related to the outcome being assessed will be excluded from the model. That is, variables will not be used as both an outcome and as a predictor in the same model. For example, discharge mRS will not be included in the models predicting treatment differences in mRS, and baseline hypertension will not be included in models assessing treatment differences in SBP. Rather, changes from baseline to the 3, 6 and 12-month visits will be assessed using contrast statements.

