Study Design. C3FIT is a multicenter, randomized, single blinded, Phase III, cluster randomized trial. Sites will be stratified by patient admission volume and geographic location; subsequently, each site will be randomized to one of two patient care management strategies: the CSC/PSC versus ISPU model.

Outcomes. C3FIT’s primary outcomes are the SIS and smRS at 12 months.

Sample Size and Population. Based on the primary outcome, the study was originally designed for a total sample size of approximately 1800 patients, with approximately 18 sites. However, due to the challenges of the COVID-19 pandemic the sample size was decreased to 1,262 and the number of sites were increased to 22. The Statistical and Data Coordinating Center (SDCC) at the University of Alabama determined the change in sample size would not influence the study statistical measures and/or study power, and our funder, PCORI, approved of the changes.

Interventions. Coordinated care (including in-home/in-patient rehabilitation and skilled nursing or extended care facility visits) will be provided based on protocol-based coordination of post-acute in-home/facility care for ISPU Site patients, while CSC/PSC patients will be managed per standard CSC/PSC protocol with no additional study related management post discharge. Clinical site personnel will be provided with training specific to the arm to which they are randomized.

Duration. Patients will be followed at the site level for one year after enrollment.

1. **STUDY OBJECTIVES**

The current standard of stroke care is the JC-certified CSC/PSC care system, a collection of proven individual processes of care, but a system that lacks coordination for the post-stroke care of patients. The C3FIT trial serves as the opportunity to assess potential impact on patient QOL and functional outcomes resulting from the improved integration of care provided by the ISPU approach.

C3FIT's overall goal is to assess if patient outcomes are improved when the CSC/PSC system is supplemented with an Integrated Stroke Practice Unit (ISPU) system of care, a patient-centric model of care involving the patient and caregiver/family that coordinates care from the acute management through the rehabilitation and recovery of the patient.

A. Hypotheses

C3FIT's *Primary Hypothesis* is that the ISPU model of care will show improved mean level SIS and smRS scores at 12 months compared to the CSC/PSC model of care.

The *Secondary Hypotheses* are:

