The total sample size for the primary outcome for this study will be approximately 1,800 patients (each arm anticipated to have approximately 900 patients with approximately 100 patients at each clinical site, although some sites will enroll up to 140 consented participants due to limited enrollment by other sites due to institutional COVID PANDEMIC issues). We have intentionally restricted clinical site participation to those Sites certified as a TJC CSC/PSC (or acting as such). This restriction is important not only to provide CSC/PSC intervention “state of the art” comparator group, but also to increase the homogeneity of Sites and, thereby, reduce intraclass correlation coefficient in the hierarchical models. We do not have information on the intraclass correlation coefficient of the SIS, but given this restriction, we would suggest it is quite small (0.01); however, for power calculations, we have conservatively assumed it is of modest size (0.05) and also provide estimates should it be large (0.10). These larger intraclass

correlations would arise if there is larger than anticipated heterogeneity of intervention effect, and that there is adequate power for these larger intraclass correlation coefficients shows that we are well-positioned to detect intervention even in the presence substantial heterogeneity of the effect. Under this assumption and with the standard deviation of the SIS being approximately 8⁴⁹, if the interclass correlation is 0.05 then mean intervention differences of 2.7 and 3.2 can be detected with 80% and 90% power respectively (power calculations by PASS, NCSS, Kayville, UT); 2.7 was chosen based on evidence from Lin et al³⁰. Even if the intraclass correlation is 0.10, differences of 3.7 and 4.3 can be detected with 80% and 90% power. As such, we have quite good power to detect clinically significant differences generally smaller than half of a standard deviation of the outcome scale.

B. Analyses

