Study Design. C3FIT is a multicenter, randomized, single blinded, Phase III, cluster randomized trial. Clinical sites were stratified by geography, balanced by patient volume, and randomized to one of two patient care management using the CSC/PSC or ISPU model.

Outcomes. C3FIT’s primary outcomes are the SIS and smRS at 12 months.

Sample Size and Population. Based on the primary outcome, the study was originally designed for a total sample size of approximately 1800 patients, with approximately 18 sites. However, due to the challenges of the COVID-19 pandemic, the sample size was decreased to 1,262, and the number of sites were increased to 23. The C3FIT Statistical and Data Coordinating Center (SDCC) at the University of Alabama Birmingham (UAB) determined that this change in samples size does not impact the study’s statistical measures and/or study power, and our funder, PCORI, approved of the changes.

Interventions. Coordinated care (including in-home/in-patient rehabilitation and skilled nursing or extended care facility visits) will be provided based on protocol-based coordination of post-acute in-home/facility care for ISPU Site patients, while CSC/PSC patients will be managed per standard CSC/PSC protocol with no additional study related management post discharge. The clinical sites will be provided with training specific to the arm to which they are randomized.

Duration. Patients will be followed at the site level for one year after enrollment.

2. **STUDY OBJECTIVES**

The current standard of stroke care is the JC-certified CSC/PSC care system, a collection of proven individual processes of care, but a system that lacks coordination for the post-stroke care of patients. The C3FIT trial serves as the opportunity to assess potential impact on patient QOL and functional outcomes resulting from the improved integration of care provided by the ISPU approach.

C3FIT's overall goal is to assess if patient outcomes are improved when the CSC/PSC system is supplemented with an Integrated Stroke Practice Unit (ISPU) system of care, a patient-centric model of care involving the patient and caregiver/family that coordinates care from the acute management through the rehabilitation and recovery of the patient.

A. Hypotheses

C3FIT's *Primary Hypothesis* is that the ISPU model of care will show improved mean level SIS and smRS scores at 12 months compared to the CSC/PSC model of care.

The *Secondary Hypotheses* are:

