### **3.3. Stroke Impact Scale (SIS)**

The SIS is a continuous outcome variable with a range from 0 to 100 which will be analyzed identically to continuous intervening factors measured at 4 timepoints (including the analysis with inverse probability weighting). We do note that: 1) after approximately half the patients were recruited, a decision was made to not collect SIS at baseline; however, it is quite reasonable to assume that this decision will give rise to data missing at random and the missingness will be addressed by the mixed models, and 2) the baseline SIS collected were the “long form” of the questionnaire (96 items); however, the 16 items in the short form used at 3, 6 and 12 months are a subset of the long form, and these items will be extracted and scored identically with the follow-up assessments. The analysis of SIS will employ analysis for a continuous factor, but will follow the modeling approach described above for mRS, specifically reporting treatment differences in mean SIS rather than treatment differences in the proportion with good mRS outcome (primary outcome as treatment difference in the change in mean SIS between baseline and 12 months, 4-level incremental models, with/without inverse probability weighting, assessment of effect modifiers, etc.).

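### No SAP model includes enrolment or discharge date, which matters most for the primary SIS change contrast because baseline SIS was stopped partway through recruitment

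*SAP*

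**What the plan says.** On covariates, SAP section 2 states: "The covariates used in the incremental models include measures of stroke severity, demographic factors, and traditional cerebrovascular risk factors". None of the listed variables is a date or calendar period. In SAP sections 3 and 4, time means visit month, time to event or time at risk. The inverse-probability weights in SAP 3.1 also omit date, and they model whether the 12-month observation is seen, not whether baseline is seen.

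On accrual, the protocol Summary (ISPU-arm part) says that "due to the challenges of the COVID-19 pandemic the sample size was decreased to 1,262 and the number of sites were increased to 22". The CSC/PSC-arm part gives 23 sites ("the sample size was decreased to 1,262, and the number of sites were increased to 23"), and the SAP Introduction gives 24 randomised and 21 with data. Protocol 9.A adds that "some sites will enroll up to 140 consented participants due to limited enrollment by other sites due to institutional COVID PANDEMIC issues".

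On baseline SIS, SAP 3.3 says that "after approximately half the patients were recruited, a decision was made to not collect SIS at baseline". It calls the resulting gap reasonably missing at random and leaves it to the mixed model. The primary SIS outcome in that section is the treatment difference in change from baseline to 12 months.

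**The concern.** Whole sites belong to one arm, so the calendar mix of patients can differ between arms if sites recruit at different times. The SAP Introduction accepts that cluster randomisation may leave key factors unbalanced and builds four incremental models for that reason, but date is in none of them. The documents report a date-related disruption that was uneven across sites.

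For SIS there is a second problem. Baseline SIS exists for earlier patients and not for later ones, so enrolment date decides who has a month-0 value. If SIS also varies with calendar period, the missing values are not at random given what is in the model. What is at stake is the validity of the standard error, and so of the p-value, for one of the two primary outcomes.

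**Working it through.** **1. The plan's own figure, used only as a yardstick.** Protocol 9.A gives 9 sites per arm, 100 patients per site, SD 8 and ICC 0.05. Two-sided 5% is assumed, as alpha is not stated. Design effect = 1 + 99 × 0.05 = 5.95. SE = 8 × √(2 × 5.95 / 900) = 0.92. With a noncentral t on 16 df, the detectable differences are 2.75 (80% power) and 3.18 (90%), matching the stated 2.7 and 3.2. At ICC 0.10 they are 3.72 and 4.30, matching 3.7 and 4.3.

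**2. How far the calendar mix can differ by chance.** The documents give no dates and no split of the 21 sites, so these inputs are assumptions: 10 versus 11 sites, site sizes 20 to 140, and an SD of 0.2 or 0.3 for the site's share of late-enrolled patients. Across random allocations the mean absolute arm difference in late share is 7.4 or 10.4 points, with a 90th percentile of 15.4 or 21.2. A 20-point difference is exceeded in about 3% or 12% of allocations. At the typical imbalance, a 4-point period effect shifts a 12-month mean by 0.074 × 4 = 0.30 or 0.104 × 4 = 0.42 points, which is 11% or 15% of 2.7.

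**3. Outcomes compared at one visit.** Simulation: 21 sites of 60, SD 8, ICC 0.05, share SD 0.2, date omitted, no systematic arm difference. Type I error is 5.1% at both a 4-point and an 8-point period effect, and mean bias is about zero. The SD of the estimate rises from 0.90 to 0.98 and 1.14. This is lost precision, not a false effect.

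**4. The SIS change contrast.** Let γ be a period effect equal at both visits, q the late share and ρ the within-patient correlation. The true change is zero and only early patients have a baseline. Measure from the early-period mean and ignore the site effect:

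- Modelled month-0 mean ≈ ρ × (month-12 mean of all − month-12 mean of early patients) = ργq. The true value is γq.
- Modelled change ≈ γq − ργq = γ(1 − ρ)q, instead of 0.
- Error in the arm difference ≈ γ(1 − ρ)(q₁ − q₀).

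This averages to zero over randomisation. It varies between sites, however, and acts as a site-by-visit effect. The planned site intercept is common to all visits and does not carry it.

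**5. Size of the understated standard error.** Added variance ≈ [γ(1 − ρ)]² × Var(q) × (1/11 + 1/10). With an assumed SD(q) of 0.25, Var(q) × 0.1909 = 0.0625 × 0.1909 = 0.0119. The model SE at ρ = 0.5 in a two-visit simulation is 0.607, a variance of 0.368.

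| γ | added variance | true SD | 1.96 × 0.607 / SD | type I error |
|---|---|---|---|---|
| 4 | 4 × 0.0119 = 0.048 | 0.645 | 1.84 | 6.5% |
| 8 | 16 × 0.0119 = 0.191 | 0.748 | 1.59 | 11.2% |

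**6. Simulation of the same contrast** (21 sites, ICC 0.05, share SD 0.25, baseline seen only early, no systematic arm imbalance). Generalised least squares without date gave about 7% and 12%. With one date term it gave about 4% to 5%, and the model SE was 0.595 against 0.594. Re-runs used ρ of 0.5 or 0.7, variance components known or estimated by REML, and equal or unequal site sizes. They gave 5.5% to 6.7% at 4 points and 7.1% to 10.0% at 8 points, against 4.4% to 5.9% with date.

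**7. If accrual did differ by arm.** With an assumed 20-point imbalance and a 4-point period effect, the formula in step 4 gives 0.20 × 4 × 0.5 = 0.40 points at ρ = 0.5 and 0.20 × 4 × 0.3 = 0.24 at ρ = 0.7. Simulation with the site effect included gave 0.32 and 0.19. With complete baseline data it would be zero. For a comparison at a single visit under the same imbalance, type I error is 12.1% without date and 5.0% with it. At a 10-point imbalance it is 6.5% and 4.8%.

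**The case against.** A reader might infer that the omission lets pandemic effects pass for an ISPU effect throughout the trial. The documents do not support that. Sites were randomised to parallel arms, stratified by geography and balanced by volume. Nothing shows that accrual timing, the added sites or the sites without data differed by arm. Chance differences between sites are between-site variance, which the site random effect carries into the standard error for single-visit comparisons (step 3). A 20-point imbalance is a tail case. For mRS, which has a baseline throughout, a period effect common to both visits largely cancels in the change. That SIS varies with calendar period at all is an assumption. All of this stands.

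It can also be said that stopping baseline SIS was a study-wide decision, so the error in the modelled baseline is shared by both arms and cancels. That is right on average and only when the calendar mix is equal. In a given trial the mix varies between sites, and steps 4 to 6 show that the planned random effects do not price that variation into the change contrast.

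Finally, a full period-by-visit interaction would be a poor remedy. After baseline collection stopped, the month-0 SIS cells are empty, so arm means at month 0 over the pooled calendar distribution cannot be estimated. Extra terms also burden models for which the SAP already foresees non-convergence. That stands too and limits the fix.

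**Conclusion.** The point holds in a limited form. No SAP model contains date. For most outcomes the cost is some precision and no protection if the realised accrual calendars differ by arm. Outcomes without a baseline, such as caregiver strain and perceived support, lack even the partial protection of a change score.

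For the SIS change contrast the cost is larger. Without date, the missing-at-random statement in SAP 3.3 is not tenable if SIS varies with calendar period, and the standard error is then too small. Type I error is about 6% to 7% at a 4-point period effect and between 7% and 12% at 8 points, against about 5% with date. These figures rest on an assumed period effect, an assumed spread of late shares across sites, and a within-patient correlation that the documents do not give. A higher correlation reduces them, and with no period effect the problem disappears. This is a worthwhile, inexpensive improvement, not evidence of a biased trial.

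**What to change.** - Add discharge date, linear or in a few calendar categories, as a main effect in the SIS mixed model, and restate the missing-at-random assumption in SAP 3.3 as conditional on date.
- Add the same term to the adjusted models for the other outcomes. In the time-to-event models with few events, use a single linear term.
- Tabulate enrolment by calendar period and arm, so that any imbalance is visible.
- Do not require a period-by-visit interaction that includes month 0 for SIS. If one is wanted, limit it to the follow-up visits as a sensitivity analysis.

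The cost is SAP wording and one or a few parameters, since SAP 4.1 already counts days from discharge. At 1,262 patients and 21 equal sites, losing one site-level degree of freedom lowers power for 2.7 points from 81.6% to 81.3%, before any collinearity of date with arm. A main effect of date does not address a pandemic effect that acts differently on the two care models.
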